13.5 Reporting and Exclusions

13.5.1 Evaluation of Toxicity

All patients will be evaluable for toxicity from the time of their first treatment with MK-2206.

13.5.2 Evaluation of Response

All patients included in the study must be assessed for response to treatment, even if there are major protocol treatment deviations or if they are ineligible. Each patient will be assigned one of the following categories: 1) complete response, 2) partial response, 3) stable disease, 4) progressive disease, 5) early death from malignant disease, 6) early death from toxicity, 7) early death because of other cause, or 9) unknown (not assessable, insufficient data). [Note: By arbitrary convention, category 9 usually designates the “unknown” status of any type of data in a clinical database.]

All of the patients who met the eligibility criteria (with the possible exception of those who received no study medication) should be included in the main analysis of the response rate. Patients in response categories 4-9 should be considered to have a treatment failure (disease progression). Thus, an incorrect treatment schedule or drug administration does not result in exclusion from the analysis of the response rate. Precise definitions for categories 4-9 will be protocol specific.

All conclusions should be based on all eligible patients. Subanalyses may then be performed on the basis of a subset of patients, excluding those for whom major protocol deviations have been identified (e.g., early death due to other reasons, early discontinuation of treatment, major protocol violations, etc.). However, these subanalyses may not serve as the basis for drawing conclusions concerning treatment efficacy, and the reasons for excluding patients from the analysis should be clearly reported. The 95% confidence intervals should also be provided.

REFERENCES

- 1 Altomare, D.A., and J.R. Testa. (2005). Perturbations of the AKT signaling pathway in human cancer. *Oncogene*. 24:7455-7464.
- 2 Cejka, D., M. Preusser, A. Woehrer, *et al.* (2008). Everolimus (RAD001) and anti-angiogenic cyclophosphamide show long-term control of gastric cancer growth in vivo. *Cancer Biol Ther*. 7:1377-1385.
- 3 Engelman, J.A., L. Chen, X. Tan, *et al.* (2008). Effective use of PI3K and MEK inhibitors to treat mutant Kras G12D and PIK3CA H1047R murine lung cancers. *Nat Med*. 14:1351-1356.
- 4 Fry, M.J. (2001). Phosphoinositide 3-kinase signalling in breast cancer: how big a role might it play? *Breast Cancer Research*. 3:304-312.

APPENDIX A PERFORMANCE STATUS CRITERIA

| ECOG Performance Status Scale | |
|--------------------------------------|---|
| Grade | Descriptions |
| 0 | Normal activity. Fully active, able to carry on all pre-disease performance without restriction. |
| 1 | Symptoms, but ambulatory. Restricted in physically strenuous activity, but ambulatory and able to carry out work of a light or sedentary nature (e.g., light housework, office work). |
| 2 | In bed <50% of the time. Ambulatory and capable of all self-care, but unable to carry out any work activities. Up and about more than 50% of waking hours. |
| 3 | In bed >50% of the time. Capable of only limited self-care, confined to bed or chair more than 50% of waking hours. |
| 4 | 100% bedridden. Completely disabled. Cannot carry on any self-care. Totally confined to bed or chair. |
| 5 | Dead. |

APPENDIX B CTEP MULTICENTER GUIDELINES

If an institution wishes to collaborate with other participating institutions in performing a CTEP sponsored research protocol, then the following guidelines must be followed.

Responsibility of the Protocol Chair

- The Protocol Chair will be the single liaison with the CTEP Protocol and Information Office (PIO). The Protocol Chair is responsible for the coordination, development, submission, and approval of the protocol as well as its subsequent amendments. The protocol must not be rewritten or modified by anyone other than the Protocol Chair. There will be only one version of the protocol, and each participating institution will use that document. The Protocol Chair is responsible for assuring that all participating institutions are using the correct version of the protocol.
- The Protocol Chair is responsible for the overall conduct of the study at all participating institutions and for monitoring its progress. All reporting requirements to CTEP are the responsibility of the Protocol Chair.
- The Protocol Chair is responsible for the timely review of Adverse Events (AE) to assure safety of the patients.
- The Protocol Chair will be responsible for the review of and timely submission of data for study analysis.

Responsibilities of the Coordinating Center

- Each participating institution will have an appropriate assurance on file with the Office for Human Research Protection (OHRP), NIH. The Coordinating Center is responsible for assuring that each participating institution has an OHRP assurance and must maintain copies of IRB approvals from each participating site.
- Prior to the activation of the protocol at each participating institution, an OHRP form 310 (documentation of IRB approval) must be submitted to the CTEP PIO.
- The Coordinating Center is responsible for central patient registration. The Coordinating Center is responsible for assuring that IRB approval has been obtained at each participating site prior to the first patient registration from that site.
- The Coordinating Center is responsible for the preparation of all submitted data for review by the Protocol Chair.
- The Coordinating Center will maintain documentation of AE reports. There are two options for AE reporting: (1) participating institutions may report directly to CTEP with a copy to the Coordinating Center, or (2) participating institutions report to the Coordinating Center who in turn report to CTEP. The Coordinating Center will submit AE reports to the Protocol Chair for timely review.
- Audits may be accomplished in one of two ways: (1) source documents and research records for selected patients are brought from participating sites to the Coordinating Center for audit, or (2) selected patient records may be audited on-site at participating sites. If the NCI chooses to have an audit at the Coordinating Center, then the Coordinating Center is responsible for having all source documents, research records, all IRB approval documents, NCI Drug Accountability Record forms, patient registration lists, response assessments scans, x-rays, etc. available for the audit.

Inclusion of Multicenter Guidelines in the Protocol

- The protocol must include the following minimum information:
 - The title page must include the name and address of each participating institution and the name, telephone number and e-mail address of the responsible investigator at each participating institution.
 - The Coordinating Center must be designated on the title page.
 - Central registration of patients is required. The procedures for registration must be stated in the protocol.
 - Data collection forms should be of a common format. Sample forms should be submitted with the protocol. The frequency and timing of data submission forms to the Coordinating Center should be stated.
 - Describe how AEs will be reported from the participating institutions, either directly to CTEP or through the Coordinating Center.
 - Describe how Safety Reports and Action Letters from CTEP will be distributed to participating institutions.

Agent Ordering

- Except in very unusual circumstances, each participating institution will order DCTD-supplied investigational agents directly from CTEP. Investigational agents may be ordered by a participating site only after the initial IRB approval for the site has been forwarded by the Coordinating Center to the CTEP PIO.

APPENDIX C LIST OF CYP3A4 INHIBITORS AND INDUCERS

CYP3A4 Inhibitors

| | | | |
|------------------|----------------------|--------------------|-----------------|
| Acetaminophen | Diclofenac | Lomustine | Primaquine |
| Acetazolamide | Dihydroergotamine | Losartan | Progesterone |
| Amiodarone | Diltiazem | Lovastatin | Propofol |
| Amlodipine | Disulfiram | Mefloquine | Propoxyphene |
| Amprenavir | Docetaxel | Mestranol | Quinidine |
| Anastrozole | Doxorubicin | Methadone | Quinine |
| Aprepitant | Doxycycline | Methimazole | Quinupristin |
| Atazanavir | Drospirenone | Methoxsalen | Rabeprazole |
| Atorvastatin | Efavirenz | Methylprednisolone | Ranolazine |
| Azelastine | Enoxacin | Metronidazole | Risperidone |
| Azithromycin | Entacapone | Miconazole | Ritonavir |
| Betamethasone | Ergotamine | Midazolam | Saquinavir |
| Bortezomib | Erythromycin | Mifepristone | Selegiline |
| Bromocriptine | Ethinyl estradiol | Mirtazapine | Sertraline |
| Caffeine | Etoposide | Mitoxantrone | Sildenafil |
| Cerivastatin | Felodipine | Modafinil | Sirolimus |
| Chloramphenicol | Fentanyl | Nefazodone | Sulconazole |
| Chlorzoxazone | Fluconazole | Nelfinavir | Tacrolimus |
| Cimetidine | Fluoxetine | Nevirapine | Tamoxifen |
| Ciprofloxacin | Fluvastatin | Nicardipine | Telithromycin |
| Cisapride | Fluvoxamine | Nifedipine | Teniposide |
| Clarithromycin | Fosamprenavir | Nisoldipine | Testosterone |
| Clemastine | Glyburide | Nizatidine | Tetracycline |
| Clofazimine | Grapefruit juice (2) | Norfloxacin | Ticlopidine |
| Clotrimazole | Haloperidol | Olanzapine | Tranlycypromine |
| Clozapine | Hydralazine | Omeprazole | Trazodone |
| Cocaine | Ifosfamide | Orphenadrine | Troleandomycin |
| Conivaptan | Imatinib | Oxybutynin | Valproic acid |
| Cyclophosphamide | Indinavir | Paroxetine | Venlafaxine |
| Cyclosporine | Irbesartan | Pentamidine | Verapamil |
| Danazol | Isoniazid | Pergolide | Vinblastine |
| Dasatinib (1) | Isradipine | Phencyclidine | Vincristine |
| Delavirdine | Itraconazole | Pilocarpine | Vinorelbine |
| Desipramine | Ketoconazole | Pimozide | Voriconazole |
| Dexmedetomidine | Lansoprazole | Pravastatin | Zafirlukast |
| Diazepam | Lidocaine | Prednisolone | Ziprasidone |

CYP3A4 Inducers

| | | | |
|-------------------|---------------|-----------|---------------------|
| Aminoglutethimide | Nevirapine | Phenytoin | Rifapentine |
| Carbamazepine | Oxcarbazepine | Primidone | St. John's wort (3) |
| Fosphenytoin | Pentobarbital | Rifabutin | |
| Nafcillin | Phenobarbital | Rifampin | |

When MK-2206 is co-administered with compounds classified as 'inhibitors', increased plasma concentrations of MK-2206 is the potential outcome. The co-administration of 'inducers' would potentially lower plasma MK-2206 concentrations.

Everolimus is a substrate of CYP3A4 and a substrate and inhibitor of P-glycoprotein. Everolimus metabolism may be affected by drugs that are substrates or strong inhibitors or inducers of CYP3A4 or P-glycoprotein.

Note: Adapted from *Cytochrome P450 Enzymes: Substrates, Inhibitors, and Inducers*. In: Lacy CF, Armstrong LL, Goldman MP, Lance LL eds. *Drug Information Handbook 15TH ed.* Hudson, OH; LexiComp Inc. 2007: 1899-1912.
Only major substrates and effective inducers are listed.

Additional information for drug interactions with cytochrome P450 isoenzymes can be found at <http://medicine.iupui.edu/flockhart/>.

(1) Investigator's Brochure: MK-2206. Merck. January 2009.

(2) Malhotra et al. (2001). *Clin Pharmacol Ther.* 69:14-23.

(3) Mathijssen et al. (2002). *J Natl Cancer Inst.* 94:1247-1249.
Frye et al. (2004). *Clin Pharmacol Ther.* 76:323-329.

Updated on May 1, 2007

APPENDIX D MEDICATIONS THAT MAY CAUSE QTC PROLONGATION

The following table presents a list of drugs that may prolong the QTc. These drugs are prohibited during the study. MK-2206 may be administered after a 5 half-life washout period elapses following the use of these drugs. Washout period is based on roughly 5 half-lives and rounded to a convenient interval.

| Compound | Compound Half Life | Possible Washout Period - Hours | Possible Washout Period - Days |
|------------------------|--|---------------------------------|--------------------------------|
| Alfuzocin | ~10 hours | | 7 |
| Amantadine | 17 +/- 4 hours (10-25) | | 4 |
| Amiodarone (cordarone) | 58 days (15-142) 36 days (active metabolite) | | 180 |
| Amitriptyline* | > 24 hours, wide interpatient variability | | |
| Arsenic trioxide | Not characterized | | |
| Azithromycin | 40 hours | | |
| Bepridil | 42 hr (26-64) | | 10 |
| Chloral hydrate | Readily converted to Trichloroethanol (active metabolite T _{1/2} =7-10 hour) | 48 | |
| Chloroquine | Prolonged (days to weeks) | | |
| Chlorpromazine | 30 +/- 7 hours | | 7 |
| Cisapride | 6 – 12 hour, up to 20 hour | 60 | |
| Clarithromycin | Non linear PK3-4 hr (250mg Q12) 5-7 hr (500mg Q12) | 36 | |
| Cloroquine | 6 to 60 days; mean 20 days | | |
| Desipramine* | > 24 hours, wide interpatient variability | | |
| Disopyramide | 6.7 hr (4-10) | 36 | |
| Dofetilide | 10 hr | 48 | |
| Dolesetron | 8.1 hr | | |
| Domperidone | 7-8 hr | 48 | |
| Doxepin* | > 24 hours, wide interpatient variability | | |
| Droperidol | 2.2 hours | 10 | |
| Erythromycin | * Each salt form has different Half life* | | |
| Felbamate | 20-23 hr | | 5 |
| Flecainide | 20 hr (12-27) | | 5 |
| Foscarnet | 87.5+/-41.8 hours *distribution and release from bone* | | 20 |
| Fosphenytoin | 12-29 hr | | 6 |
| Gatifloxacin | 7-14 hr | 48 | |
| Gemifloxacin | 7 hours | 48 | |
| Grepafloxacin | 16 hr | | 3 |
| Halofantrine | 6-10 days (variable among individual) | | 45 |
| Haloperidol | 18 +/-5 hr | | 5 |
| Ibutilide | 6 hours (2-12) * variable among subject* | 36 | |
| Imipramine* | > 24 hours, wide interpatient variability | | |
| Indapamide | 14 hours (biphasic elimination) | | 3 |
| Isradipine | 8 hours (multiple metabolites) | 48 | |
| Levofloxacin | 6-8 hours | 48 | |
| Levomethadyl | Multiple compartment PK with active metabolite 2.6 day for LAAM, 2 day for nor-LAAM, 4 day for dinor-LAAM | | 20 |

| Compound | Compound Half Life | Possible Washout Period - Hours | Possible Washout Period - Days |
|----------------|--|---------------------------------|--------------------------------|
| Lithium | 24 hour (10-50) | | 7 |
| Mesoridazine | 24-48 hours (animal study) | | 10 |
| Methadone | 15-30 hours | | 7 |
| Moexipril/HCTZ | 2-9 hour (include active metabolite) for moexipril; 5.6-14.8 hours for HCTZ | 48 | |
| Moxifloxacin | 12 +/-1.3 hours | 72 | |
| Naratriptan | 6 hours | 36 | |
| Nicardipine | ~ 2 hour post IV infusion | 12 | |
| Nortriptyline* | > 24 hours, wide interpatient variability | | |
| Octreotide | 1.7 hours | 12 | |
| Ofloxacin | 5 to 7.5 hours | | 2 |
| Ondansetron | 4 hours (IV/IM); 3 hours (PO) | | 1 to 3 |
| Pentamidine | 6.4+/-1.3 hours | 36 | |
| Pimozide | 55 hours | | 10 |
| Procainamide | 3-4 hour for PA and NAPA (active metabolite) | 24 | |
| Protiptyline* | > 24 hours, wide interpatient variability | | |
| Quetiapine | 6 hours | 36 | |
| Quinidine | 6-8 hours in adult; 3-4 hours in children | 36 | |
| Quinine | 4-5 hours | | |
| Risperidone | 3-20 hours (extensive to poor metabolizer) 9-hydroxyrisperidone (active metabolite) T _{1/2} =21-30 hours (extensive to poor metabolizer) | | 4 |
| Salmeterol | 5.5 hours (only one datum) | 36 | |
| Sotalol | 12 hours | 72 | |
| Sparfloxacin | 20 hours (16-30) | | 4 |
| Sumatriptan | 2.5 hours | 12 | |
| Tacrolimus | ~34 hours in healthy; ~19 hours in Kidney transplant | | 7 |
| Tamoxifen | 5-7 days (biphasic) | | 30 |
| Telithromycin | 2-3 hr | 24 | |
| Thioridazine | 20-40 hours (Phenothiazines) | | 7 |
| Tizanidine | 2.5 hours | 12 | |
| Vardenafil | 4 to 5 hours | | |
| Venlafaxine | 5 +/-2 hours for parent comp. 11+/-2 hours for OVD (active metabolite) | 60 | |
| Voriconazole | 6 hours; dose dependent | | |
| Ziprasidone | 7 hr | 36 | |
| Zolmitriptan | 2.8-3.7 hours (higher in female) | 18 | |

* Weakly associated with Torsades de Pointes and/or QT prolongation but that are unlikely to be a risk for Torsades de Pointes when used in usual recommended dosages and in patients without other risk factors (e.g., concomitant QT prolonging drugs, bradycardia, electrolyte disturbances, congenital long QT syndrome, concomitant drugs that inhibit metabolism).

References:

1. Physician's Desk Reference 2002
2. Facts and Comparisons (update to June 2005)
3. The Pharmacological Basis of Therapeutics 9th Edition, 1996

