3.2 Exclusion Criteria

- 3.2.1 Patients who received oral TKIs (sorafenib, sunitinib, or pazopanib) within 2 weeks prior to entering the study, radiotherapy, immunotherapy or chemotherapy within 4 weeks prior to entering the study, bevacizumab within 4 weeks prior to entering the study, or those who have not recovered from adverse events due to agents administered more than 4 weeks earlier (recovered to \leq Grade 1).
- 3.2.2 Patients may not be receiving any other investigational agents. Patients may not have received an mTOR inhibitor.
- 3.2.3 Patients with known brain metastases should be excluded from this clinical trial because of their poor prognosis and because they often develop progressive neurologic dysfunction that would confound the evaluation of neurologic and other adverse events.
- 3.2.4 History of allergic reactions attributed to compounds of similar chemical or biologic composition to MK-2206 or other agents used in the study.
- 3.2.5 Patients receiving any medications or substances that are strong inhibitors or inducers of CYP 450 3A4 are ineligible. Lists including medications and substances known or with the potential to interact with the CYP 450 3A4 isoenzymes are provided in [Appendix C](#).

- 3.2.6 Patient should have a Hemoglobin A1C value of < 8%. Preclinical studies demonstrated the potential of MK-2206 for induction of hyperglycemia in all preclinical species tested. Studies also demonstrate a risk of hyperglycemia, hyperlipidemia and hypertriglyceridemia associated with everolimus therapy. Patients with diabetes or in risk for hyperglycemia, hyperlipidemia and/or hypertriglyceridemia should not be excluded from trials with MK-2206 or everolimus, but the patient should be well controlled on oral agents (recent (i.e. within 3 months) HbA1C \leq 7.0) before the patient enters the trial.
- 3.2.7 Preclinical studies indicated transient changes in QTc interval during MK-2206 treatment. Prolongation of QTc interval is potentially a safety concern while on MK-2206 therapy. Cardiovascular: baseline QTcF > 450 msec (male) or QTcF > 470 msec (female) will exclude patients from entry on study. A list of medications that may cause QTc interval prolongation are listed in [Appendix D](#), and should be avoided by patients entering on trial.

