5.3 General Concomitant Medication and Supportive Care Guidelines

Because MK-2206 is metabolized by CYP3A4, the case report form must capture the concurrent use of all other drugs, over-the-counter medications, or alternative therapies. The Principal Investigator should be alerted if the patient is taking any agent known to affect or with the potential to affect selected CYP450 isoenzymes. A list of agents known to interact with the CYP3A4 isoform is listed in [Appendix C](#).

Drugs known that may prolong the QTc interval should be avoided.

Everolimus is a substrate of CYP3A4 and a substrate and inhibitor of P-glycoprotein. Everolimus metabolism may be affected by drugs that are substrates or strong inhibitors or inducers of CYP3A4 or P-glycoprotein. A list of agents known to interact with the CYP3A4 and P-glycoprotein are listed in [Appendix C](#).

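### Section 5.3 is weaker than the Appendix D ban on QTc-prolonging drugs, and the 180-day amiodarone washout covers only 3.1 half-lives of the parent drug

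*Combined protocol and SAP*

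**What the plan says.** Three places deal with drugs that may prolong QTc.

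- **Appendix D** heads its table with a ban, "These drugs are prohibited during the study", and a washout rule: "MK-2206 may be administered after a 5 half-life washout period elapses following the use of these drugs". It explains the table cells this way: "Washout period is based on roughly 5 half-lives and rounded to a convenient interval".
- **Section 3.2.7** (exclusion criteria) points to the Appendix D list and says of those drugs "and should be avoided by patients entering on trial". It states no interval itself.
- **Section 5.3** (concomitant medication) says "Drugs known that may prolong the QTc interval should be avoided". It gives no interval and does not cite Appendix D, although the neighbouring CYP3A4 text in the same section does cite Appendix C.

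The amiodarone row of Appendix D gives the half-life as "58 days (15-142) 36 days (active metabolite") and the possible washout as 180 days.

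**The concern.** Section 3.2.7 names QTc prolongation as a potential safety concern on MK-2206. Section 2.2 reports grade 1/2 prolongation in 14 of 64 patients with ECG data (21.9%) and one grade 3 case at 135 mg weekly, below this trial's 200 mg starting dose. The same section calls the episodes generally isolated, not apparently dose-dependent and not clinically significant. The written safeguard should therefore say one thing throughout and follow its own rule.

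It falls short in two ways. First, the section a clinician consults during treatment is weaker than the appendix. The situation is foreseeable: section 7.1.1 lists nausea as likely (above 20%) on MK-2206, and section 2.2 mentions oral antibiotics in supportive care for rash. Appendix D includes ondansetron, levofloxacin and moxifloxacin. (That these are an antiemetic and two antibiotics is general knowledge, not protocol text.) A clinician who reads 5.3 as allowing such a drug when needed departs from Appendix D. Appendix K has auditors check compliance and deviation reporting, so sites need one rule.

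Second, a site that follows the printed amiodarone cell may start MK-2206 well before five half-lives of the parent have passed.

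**Working it through.** **Step 1. The texts side by side.**

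| Place | Strength | Washout | Cites Appendix D |
|---|---|---|---|
| Appendix D | Prohibited during the study | Five half-lives before MK-2206 | (is the list) |
| 3.2.7, at entry | Advice to avoid | By cross-reference only | Yes |
| 5.3, on treatment | Advice to avoid | None | No |

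At entry the gap is narrow. Section 3.2.7 is an exclusion criterion that points to the list, and this protocol also words firm eligibility requirements with 'should' (3.1.1, 3.2.3, 3.2.6). The real gap is in 5.3.

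**Step 2. Reproduce the printed 180 days.** Inputs from the amiodarone row: parent half-life 58 days (range 15-142), active metabolite 36 days, washout 180 days. The rule is washout = 5 x half-life.

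- Active metabolite: 5 x 36 = 180 days, which matches the cell exactly.
- Parent: 5 x 58 = 290 days, which does not match.

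**Step 3. What 180 days means for the parent.** Number of half-lives = washout / half-life. Fraction remaining = 2^-(washout / half-life), assuming simple first-order decay.

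- 180/58 = 3.10 half-lives; 2^-3.10 = 11.6% remaining.
- Five half-lives: 2^-5 = 3.1% remaining.
- Shortfall: (290 - 180)/290 = 38%.

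Over the printed half-life range:

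| Parent half-life | Five half-lives | Remaining at 180 days |
|---|---|---|
| 15 days | 75 days | 2^-(180/15) = 0.02% |
| 58 days | 290 days | 11.6% |
| 142 days | 710 days | 2^-(180/142) = 41.5% |

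At a 142-day half-life even 290 days leaves 2^-(290/142) = 24.3%. So 290 is the value the rule gives at the central half-life, not a bound for every patient.

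**Step 4. Could rounding explain it?** Take the central half-life of the slowest listed moiety in each row (the midpoint where only a range is printed). Of 69 rows, 54 print a washout, and 12 of those fall below five half-lives. Nine lie between 4.5 and 4.94, which rounding covers. The other three are pimozide 240 h/55 h = 4.36, risperidone 96 h/25.5 h = 3.76 and amiodarone 3.10, the lowest in the table.

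**Step 5. Which moiety do other rows use?**

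- Levomethadyl lists "2.6 day for LAAM, 2 day for nor-LAAM, 4 day for dinor-LAAM" and prints 20 days: 20/4 = 5.0 of the slowest.
- Venlafaxine lists 5 h for the parent and 11 h for the metabolite, and prints 60 h: 60/11 = 5.45 of the slower.
- Risperidone prints 4 days against a metabolite at 21-30 h: 96/21 = 4.57 to 96/30 = 3.2, so it settles nothing.

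Two rows with more than one moiety clearly follow the slowest. Amiodarone follows the faster one.

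**The case against.** The strongest reply is that the documents already contain the right rule. Appendix D bans the drugs throughout the study, 5.3 permits nothing, and a site that avoids the drugs satisfies both texts. That is true, and it keeps the point small. It does not remove the need for 5.3 to carry the ban it is meant to implement, or at least to cite it.

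On amiodarone, the 180 days is not arbitrary: it is exactly five half-lives of a listed active moiety. The column is headed as a possible washout, the rule is approximate, and no sentence says that the slowest moiety governs. All of that stands. But the parent is the listed compound, and an approximate, rounded rule does not stretch from five half-lives to 3.1.

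Reach is also very limited. The cell changes a decision only for someone who stopped amiodarone between 180 and 290 days before MK-2206. That person must also pass the QTcF limits in 3.2.7 and the uncontrolled-illness exclusion in 3.2.8, which names cardiac arrhythmia. Section 2.2 says to keep patients with heart disease off MK-2206 trials, and amiodarone's place in Appendix C triggers the alert to the Principal Investigator in 5.3. ECGs follow on cycle 1 day 1 and every eight weeks. These shrink the group, though none is an absolute bar on the drug.

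A reader might infer more than the documents support:

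- *That entry is open to these drugs.* Section 3.2.7 points to Appendix D, so the ban and washout are reached by cross-reference.
- *That the 15 rows with no printed interval have no washout.* The general five-half-life rule in Appendix D applies to them wherever a half-life is listed.
- *That the table is unreliable as a whole.* Nine of the 12 low rows are ordinary rounding, pimozide is arguably within the approximation, and risperidone's low figure depends on the midpoint of a range.

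**Conclusion.** The point holds as a minor safety correction. Section 5.3 states less than the prohibition in Appendix D and does not cite it. The amiodarone washout is 110 days short of the appendix's own rule at the central parent half-life: 3.1 half-lives instead of five, with 11.6% remaining instead of 3.1%.

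The residual percentages assume first-order decay at the printed 58-day half-life, and the 15-142 day range makes them widely variable between patients. The documents do not link any residual level to QTc risk, so a claim that patients face a measurable arrhythmia hazard would go too far. They also give no count of affected patients; few are expected. Nothing here touches PFS, alpha or power.

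A reader might also infer that the ban ought to be confined to the MK-2206 arm, because the washout sentence names only MK-2206 and section 2.3.3 reports no preclinical QT effect for everolimus, or that the starred drugs should be exempt. Appendix D as written bans every listed drug during the study. Either change would relax it and is a separate choice for the sponsor.

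**What to change.** 1. **Amiodarone cell.** Change 180 days to about 290 days (5 x 58), note that the printed range implies 75-710 days, and add a line to Appendix D that the slowest listed moiety governs.
2. **Sections 5.3 and 3.2.7.** Replace the advice to avoid with a statement that the Appendix D drugs are prohibited, subject to the Appendix D washout before MK-2206, and cite Appendix D in 5.3.

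The cost is two reworded sentences, one added line and one table cell. A rare patient who stopped amiodarone 180-290 days earlier would wait or be excluded, and some patients may need a substitute drug during treatment. The sample size and analysis plan do not change.
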